8.7.2 Planned Analyses

Depending on the sample size, the endpoint will be assessed overall, by region and among subgroups of patients/carers.

In a first step, calculations will be performed on raw data for the overall sample. No projection factor will be applied to generalize the results to the entire prescriber's universe. As a consequence, the line "Overall - unweighted results" will show only the results observed on the overall sample and will not reflect the countries' universe since this sample is not proportional to the size of the lists in each country.

If possible, in a second step, the results will be weighted according to the real proportion of HCPs and patients/carers in each country in order to accurately reflect the population that the survey seeks to measure.

8.7.3 Analysis of Response Rate

The response rates will be calculated. In particular, the following different cases will be distinguished:

- *Selected HCPs (S): HCPs who were selected to be contacted from IQVIA OneKey lists: $S = U + RE$*
- *Unreachable HCPs (U): HCPs who were selected to be contacted from IQVIA OneKey lists but were unreachable (e.g., due to invalid contact information)*
- *Reachable HCPs (RE): HCPs who were reachable and received the invitation to participate in the survey: $RE = N + C + P + R + NE$*
- *Non-respondent HCPs (N): HCPs who were reachable but did not respond to the invitation to participate in the survey*
- **HCPs with completed questionnaires (C): HCPs who completed the entire questionnaire**
- *HCPs with partially-answered questionnaires (P): HCPs who partially completed the questionnaire (provided answers to the questionnaire but never completed/submitted it)*
- **HCPs who refused to participate (R): HCPs who explicitly indicated their refusal to participate**
- *Non-eligible HCPs (NE): HCPs who were confirmed to be non-eligible to participate in the survey after reaching out to them (e.g., retired)*

The HCP participation in the survey will be examined *in particular* as follows:

- Complete response rate = $\frac{C}{RE-NE}$
- Partial response rate = $\frac{P}{RE-NE}$
- Response rate = $\frac{C+P}{RE-NE}$
- Refusal rate = $\frac{R}{RE-NE}$

The participation rates will be presented by region and by speciality.

8.7.4 Questionnaire Analysis

Analysable questionnaires are those completed and submitted by the participants on the web. If the questionnaire is just filled on the web but not submitted, the questionnaire will not be analysed and will be discarded.

Analysis will be done on questions common to all HCPs and patients/carers as well as on a limited number of questions presented to the subgroup of patients with concomitant use of aPCC and Hemlibra® (or their carers).

For each question, the number and percentage of participants correctly answering each question will be presented. Individual awareness, knowledge, and adherence values will be calculated as the percentage of correctly answered questions; values will range from 0 to 100% with 100% representing the percentage of all questions in the category being answered correctly.

Awareness questions

- HCP questionnaire: Q8 and Q9
- Patient/carer questionnaire: Q1 and Q2

Knowledge questions

- HCP questionnaire: Q10, Q11, and Q12
- Patient/carer questionnaire
 - All: Q3, Q4, Q5, and Q6

Adherence questions

- HCP questionnaire: Q13, Q14, Q15, Q16, and Q17
- Patient/carer questionnaire
 - All: Q11
 - Additional questions for patients (or their carers) taking aPCC and Hemlibra: Q8, Q9, and Q10

In a first step, calculations will be performed on raw data. No projection factor will be applied to generalize the results to the entire prescribers' universe. As a consequence, the line "Overall - unweighted results" will show only the results observed on the overall sample and will not reflect the geographies' universe since this sample is not proportional to the size of the lists in each geography.

If possible, in a second step, the results will be weighted according to the real proportion of HCPs or patients/carers in a geographical region in order to accurately reflect the population that the survey seeks to measure.

Possible *participation* bias will be assessed by comparing the distributions of available characteristics (e.g., geography, type of setting [e.g., haemophilia treatment centre or HCCC], and speciality, if applicable and feasible) between respondents and non-respondents.

Assessment of success

The proportions of correct and appropriate answers to selected questions asked in the questionnaire will be presented for HCPs or patients/carers who provided answers to those questions, as outlined below.

Successful outcomes for the effectiveness of risk minimisation measures in the aspects of awareness, knowledge, and adherence are defined a priori by the following target levels:

For HCPs

- Awareness: Proportion of HCPs aware of the Hemlibra® educational program (Q8 and Q9) – Success: $\geq 75\%$
- Knowledge: Proportion of HCPs with knowledge of the important identified risks and potential risks associated with Hemlibra treatment (Q10, Q11, and Q12) – Success $\geq 60\%$
- Adherence: Proportion of HCPs self-reporting adherence to the additional RMMs for Hemlibra (Q13, Q14, Q15, Q16, and Q17) – Success $\geq 75\%$

For patients/carers

- Awareness: Proportion of patients/carers aware of the of the Hemlibra® educational program (Q1 and Q2) – Success: $\geq 60\%$
- Knowledge: Proportion of patients/carers with knowledge of the important identified risks and potential risks associated with Hemlibra treatment (Q3, Q4, Q5, and Q6) – Success: $\geq 60\%$
- Adherence: Proportion of patients/carers self-reporting adherence to the additional RMMs for Hemlibra (Q11) – Success: $\geq 60\%$

- Proportion of patients taking aPCC and Hemlibra (or their carers) self-reporting adherence to the additional RMMs specific for use of aPCC and Hemlibra (Q8, Q9, and Q10) - Success: $\geq 60\%$

Overall success is defined as success on all three domains measures (awareness, knowledge and adherence) for both HCPs and patients/carers.

Exploratory analysis of HCPs with higher success rates will also be performed and the percentage of HCPs who answered 80% and 90% of the questions correctly in each of domain will be calculated.

A sensitivity analysis will be performed to assess and compare the results of HCPs who were investigators in Hemlibra clinical studies (i.e., HAVEN) with the ones from HCPs who have prescribed Hemlibra exclusively in routine clinical practice.

Profile of HCPs with incorrect answers

The profile of HCPs with incorrect answers to the questions related to the three success factors will be described using all available and relevant HCPs characteristics collected in the survey (e.g., geography, speciality, duration of practice, practice setting) and past experience with Hemlibra® (number of patients prescribed).

Profile of patients with incorrect answers

The profile of patients with incorrect answers to the questions related to the three success factors will be described using all available and relevant patient characteristics collected in the survey (e.g. geography, age, diagnosis with inhibitors).

Note that other additional analyses will be performed. These include the comparison of the knowledge and adherence to additional RMMs of HCPs and patients that are aware of the additional RMMs as opposed to those who are not aware of the RMMs.

Analyses will be defined in more detail in the SAP and final report.

Note that the selection of these thresholds for success is subjective (7 May 2015 PRAC Rapporteur PASS Protocol Assessment Report; Procedure no.: EMEA/H/C/000387/MEA 087.2) and not based on a priori knowledge, experience, or established scientific criteria in the education or risk communication or evaluation literature. Therefore, the results will be contextualized considering other available information.

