8.4.1 Identification of HCPs and Patients

HCPs will be identified from a combination of public information on haemophilia treatment centre locations listed on the Haemophilia Central website and proprietary IQVIA OneKey lists. OneKey is the most comprehensive worldwide database of healthcare professionals, is representative of the HCPs population in the selected countries, and has specialties, addresses and contact information for HCPs.

To create a recruitment list of HCPs treating patients with haemophilia, addresses of haematologists from OneKey will be cross-referenced with addresses of haemophilia treatment centres and Haemophilia Comprehensive Care Centres. All haematologists working in these haemophilia treatment centres will be considered the recruitment population, since all could have potentially prescribed Hemlibra®. A screening question in the HCP questionnaire will verify that the HCP has, in fact, prescribed Hemlibra® to patients outside clinical trials. If a study country has guidelines that restrict Hemlibra® to certain locations, such as in a Comprehensive Care Centre, recruitment will focus on those locations in that country.

HCPs will be invited to participate in the survey until at least 40 completed HCP questionnaires have been returned or the list is exhausted (see Section 8.4.2).

Patients or their carers will be recruited via *their* physicians and will remain anonymous.

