8.4.2 Data Collection

Questionnaire

Both the HCP and the patient questionnaire will include multiple-choice and closed-ended questions as appropriate, to collect information on their awareness of the Hemlibra® educational program, knowledge of important identified risks (TMAs and TEs) and potential life-threatening bleeding risks associated with Hemlibra® use, and self-reported adherence to additional RMMs.

The questionnaires will be translated into the relevant local languages. Translation will be done using the forward and *backward* method of translation (i.e., from English into local language and then from local language into English). The HCP questionnaire will be tested by a sample of physicians for clarity, and the patient questionnaire will be tested by a sample of non-physicians to check the understandability of language.

Completion of the HCP and patient questionnaires is estimated to take about 15 and 10 minutes each, respectively.

Conduct of survey

The data collection period is planned for approximately 12 months. Data collection is expected to be conducted between Q1 and Q4 2020. The fieldwork start date may vary by country based on the date of local market launch and the date of any necessary EC decisions.

To ensure comprehension of the invitation and the survey, outreach will be conducted in the local country language. The survey and invitation as well as any reminders will be translated by native speakers of the respective language at IQVIA Primary Intelligence.

Prescribers (HCPs)

HCPs will be randomly contacted by emails or phone calls, when needed. Their recruitment will be done as follows:

- HCPs will be invited to participate in the survey via emails or phone calls. The survey background and objectives, the requirement to have prescribed Hemlibra® at least once prior to the study, the contact information for questions, and the proposed compensation will be explained to the HCPs at this step. IQVIA will ensure that the compensation is in line with relevant guidelines of each country and that it only constitutes a compensation for the actual effort and time that is needed to complete the questionnaire
- If they agree to participate in the survey, they will click on the link included in the email to access the questionnaire and the instructions for the online questionnaire's completion

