 - HCPs can also choose to participate in the survey by phone in the local language. In this case, an appointment for a phone interview will be scheduled with them.
- Screening questions included at the start of the questionnaire include that HCPs must have prescribed Hemlibra® at least once prior to the study and are not employed by Roche or IQVIA
- Once HCPs have passed the screening questions of the questionnaire, they are moved through the questions one question at a time. For the web-based questionnaire, HCPs can only progress to the next question when the previous question was answered, and only wholly completed questionnaires can be

submitted. If a phone interview is requested, the interviewer will complete the online questionnaire with the HCP.

- If the questionnaire is not completed within one week, the HCPs will be sent a reminder by email one week after the link was sent to them
- If the study sample size is not achieved in the country, a second reminder by phone will be conducted 1.5 weeks after the link has been sent.
- If the questionnaire is still not fully completed, a third and final reminder will be sent to the HCPs by email approximately three weeks after the start of the questionnaire.

For each HCP of the sample, the number of contacts and the date and time when he/she completed the online questionnaire will be recorded. An HCP will be considered as unreachable if he/she has been contacted between 3 and 5 times without having received any answer.

The recruitment in each country will be stopped when the target is reached. If the HCP list has been exhausted in any particular country, the recruitment in this country will be prematurely ended and a strategy will be determined to adjust the sample size with associated weighting.

Patients

HCPs that agree to participate in the patient survey will be sent informational material (kits) for distribution to up to 18 of their patients. The kit will include an explanation of the study and a simplified guide for taking the online questionnaire.

A pre-printed random unique number on the kit is registered by the HCP on a tracking web site. Tracking kit numbers allows monitoring of the number of patient questionnaires coming from the same practice. No log would be kept at the physician level which would link the kit number and the patient's identity.

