8.9 LIMITATIONS OF THE RESEARCH METHOD

Bias

The potential for selection bias of physicians participating in a survey is an inherent bias/limitation to any study based on volunteer participation. For instance, it is possible that HCPs willing to participate in the study are those with the highest awareness of the risks associated with Hemlibra®. In order to quantify any selection bias, the distribution of each stratification criterion of physicians (country, speciality, and the other available characteristics present in the screening log) will be compared between participants and non-participants.

Additionally, non-response bias may also be introduced into the study if targeted HCPs have activated filters in their mailbox that block spam and unsolicited emails. Having multiple email addresses could also affect responsiveness, especially if the one used for sending the invitation is not the primary address. HCPs who do not check their email frequently might not receive the invitation during the recruitment period. These are among the reasons why the HCPs will also be contacted by phone.

Moreover, online surveys may promote information bias that may result from social desirability, which refers to the tendency of physicians to give socially desirable/expected responses instead of choosing those reflecting their current knowledge or behaviour, e.g. physicians can copy-paste or refer to information gathered online instead of giving their own opinions ([Wyatt 2000](#)).

Social desirability can affect the validity of survey research findings, but the use of pre-populated items in the questionnaire could/tends to reduce this bias ([Nederhof 1985](#)).

Theoretically, the social desirability bias may also arise when the patients are recruited by the same HCP who has participated in the survey. There is also a potential for a HCP who participated in the survey to increase the awareness of his or her patients about the topic covered in the survey. However, due to the anonymity of the survey, the competitive recruitment (the HCP will not be certain if a patient questionnaire will ultimately be considered in the study), and the fact that the results of the patient survey will not be analysed per centre but as separate samples, this limitation is less likely to happen. As a result, we do not consider it necessary to distinguish between HCPs who participate in the survey from those who recruit patients.

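### The HCP participation-bias check compares confirmed Hemlibra prescribers with non-repliers of unknown prescribing status, so it confounds eligibility with willingness to take part

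*Protocol*

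**What the plan says.** - **Contact list (Protocol 8.4.1).** "All haematologists working in these haemophilia treatment centres will be considered the recruitment population, since all could have potentially prescribed Hemlibra". Prescribing status is not known at selection.
- **How eligibility is established (8.4.1, 8.4.2).** "A screening question in the HCP questionnaire will verify that the HCP has, in fact, prescribed Hemlibra® to patients outside clinical trials". The invitation already discloses "the requirement to have prescribed Hemlibra® at least once prior to the study". The survey questions come after the screen: "Once HCPs have passed the screening questions of the questionnaire, they are moved through the questions one question at a time".
- **Response categories (8.7.3).** Reachable HCPs are RE = N + C + P + R + NE. N are "HCPs who were reachable but did not respond to the invitation to participate in the survey". NE are "HCPs who were confirmed to be non-eligible to participate in the survey after reaching out to them", with retirement as the example. All four participation rates use RE-NE as denominator.
- **The bias check (8.7.4, 8.9).** Possible participation "bias will be assessed by comparing the distributions of available characteristics" of respondents and non-respondents: geography, type of setting and speciality, if applicable and feasible. Section 8.9 gives the purpose as quantifying selection bias. There, country, speciality and other screening-log characteristics "will be compared between participants and non-participants".

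**The concern.** The two groups differ in eligibility by construction. An HCP who completes the questionnaire has passed the prescribing screen. An HCP who stays silent may be a prescriber who declined or a non-prescriber who had nothing to answer. Sections 8.7.4 and 8.9 neither restrict the second group to prescribers nor adjust for its unknown status, and section 8.9 does not list this among the limitations.

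If prescribing differs across the compared characteristics, the difference in mix reflects both who prescribes and who chose to reply. The protocol gives reason to expect variation: section 8.4.1 foresees national restrictions to certain locations, and section 8.5.2 refers to differing market uptake and treatment concentration between countries.

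What is at stake is interpretation. Section 8.9 calls volunteer bias inherent and suggests that the more risk-aware HCPs may be those who take part. That would push scores up towards the HCP success thresholds of 75%, 60% and 75%. A reader will look to this check for reassurance, and it can mislead in either direction.

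**Working it through.** **Plan's own figure.** Section 8.5.1: 40 completes at a 10% response rate need 40/0.10 = 400 invitations. This reproduces and sets the scale below. The point disputes no stated figure.

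**Assumptions.** The documents give no prescribing or answering rates by setting, so all rates below are assumed. Take 400 reachable HCPs, 200 in comprehensive care centres (CCC) and 200 elsewhere. Partial completers are ignored and refusers are counted with the silent.

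**1. No participation bias: every prescriber takes part with probability 20%, and no non-prescriber is identified.**
- Prescribing 80% vs 30%: respondents 200×0.8×0.2 = 32 and 200×0.3×0.2 = 12, so CCC share 32/44 = 72.7%. Non-respondents 168 and 188, so 168/356 = 47.2%. False gap 25 points.
- Prescribing 60% vs 40%: respondents 24 and 16 (60.0%); non-respondents 176 and 184 (48.9%). False gap 11 points.
- Equal prescribing (50%/50% or 90%/90%): gap 0.
- Against eligible non-respondents only, the gap is 0 in every case.

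**2. Effect of the NE category (80% vs 30% case).** Moving 10%, 50% or 100% of non-prescribers to NE makes the non-respondents' CCC share 164/338 = 48.5%, 148/266 = 55.6% or 128/176 = 72.7%. The artefact vanishes only if all are identified.

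**3. Real participation bias: prescribers take part at 20% (CCC) vs 40% (elsewhere), prescribing 80% vs 30%.** Respondents 32 and 24 (57.1%). Planned comparator 168 and 176 (48.8%), a gap of +8 points. Eligible non-respondents 128 and 36 (78.0%), a gap of -21 points. The sign reverses.

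**4. Response rate.** Everyone answers with probability 30%, so the true rate among prescribers is 30%.

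| Prescribers on list | C | NE | C/(RE-NE) |
|---|---|---|---|
| 40% | 160×0.3 = 48 | 240×0.3 = 72 | 48/328 = 14.6% |
| 60% | 240×0.3 = 72 | 160×0.3 = 48 | 72/352 = 20.5% |
| 80% | 320×0.3 = 96 | 80×0.3 = 24 | 96/376 = 25.5% |

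**5. How far regrouping helps.** Compare all who answered the screen with all who did not. Prescribing 80% vs 40%, prescribers answer at 30%, no participation bias. Respondents are 48 and 24 (66.7%).
- Non-prescribers also answer at 30%: screened out 12 and 36; silent 140 and 140. Planned check 66.7% vs 50%, a false gap of 17 points. Regrouped: 60 and 60 vs 140 and 140, gap 0.
- Non-prescribers answer at 5%, because the invitation tells them they do not qualify: screened out 2 and 6; silent 150 and 170. Planned check 66.7% vs 46.9%, about 20 points. Regrouped: 50 and 30 (62.5%) vs 46.9%, still about 16 points.
- If no non-prescriber answers, the regrouped comparison equals the planned one.

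**6. Adjusted response rate in the 5% case.** Use C/[C + P + q(N + R)], where q is the assumed eligible share among HCPs who did not take part; q = 1 gives C/(RE-NE).
- q = 1: 72/392 = 18.4%.
- q as observed among those who answered, 72/80 = 0.90: 72/(72 + 0.90×320) = 72/360 = 20.0%.
- q at its true value here, (112 + 56)/320 = 0.525: 72/(72 + 168) = 30.0%.

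The observed share moves the rate the right way but not far, so a range of q is needed.

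**The case against.** - **The list is already narrowed.** It is cross-referenced to haemophilia centres. Where national guidelines restrict Hemlibra to certain locations, recruitment focuses there, which is a safeguard. Confirmed ineligible HCPs go to NE. All this stands and shrinks the artefact. It does not remove it, or no screening question would be needed.
- **A reader might infer that the check measures who prescribes and says nothing about participation.** The documents do not support that. The comparison measures a mixture, and with uniform prescribing across the compared features the artefact is zero. No prescribing rates are given, so its actual size is unknown.
- **A reader might also infer that regrouping cures the problem.** It does so only if non-prescribers answer as often as prescribers, which the disclosed prescribing requirement makes doubtful.
- **Detail belongs in the SAP.** Sections 8.7.4 and 8.9 do not map respondents or participants onto C, P, N, R and NE, and section 8.7.3 lists its rates as examples, so more may be added. But the protocol itself states the groups to be compared and the denominators. Whether non-respondents are N alone or N + R, their eligibility remains unknown.
- **Nothing decisive depends on it.** The analyses are descriptive, the check feeds no threshold, score or weight, and an understated response rate errs cautiously. This stands and limits the weight of the point. Section 8.7.3 also plans rates by region and speciality, but these share the denominator problem.

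**Conclusion.** The concern holds in this form: the check confounds eligibility with willingness to take part wherever prescribing varies by geography, setting or speciality, so neither a difference nor its absence can be read as participation bias. Under assumed rates the false gap runs from 0 (uniform prescribing) to 25 points, and one scenario turns a true -21 points into +8. C/(RE-NE) is a lower bound on the response rate among eligible HCPs, because RE-NE keeps silent HCPs who never prescribed; the illustrated 15% to 26% against a true 30% rests on the assumed eligible share. The structural part follows from the protocol's own text, while every magnitude is an assumption. It is worth correcting because section 8.9 relies on this check to quantify selection bias, but it leaves the awareness, knowledge and adherence proportions unchanged.

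**What to change.** 1. **8.7.3:** Count HCPs screened out as non-prescribers separately from other NE, such as retired HCPs.
2. **8.7.4 and 8.9:** Keep the planned comparison. Add, as a sensitivity analysis, all HCPs who answered the screen (C + P + screened-out non-prescribers) against N + R, on the same characteristics.
3. **8.7.3:** Next to C/(RE-NE), report response rates with N and R multiplied by a range of assumed eligible shares, including the share observed among those who answered the screen. Describe C/(RE-NE) as a lower bound for eligible HCPs.
4. **8.9:** State that the eligibility of non-respondents is unknown and that, because the invitation discloses the prescribing requirement, non-prescribers may answer less often, so the regrouping can reduce the artefact but does not remove it.

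The cost is wording and a little extra programming. The added rates rely on an assumed eligible share, which is why a range is needed. The protocol pools all ineligible HCPs in one class and does not say that screen failures are counted separately, so item 1 depends on the screening outcome having been stored; items 3 (with assumed shares only) and 4 can be done regardless.
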